	n=2	n=3	n=4	n=5	n=6	n=7	n=8	n=9	n=10	n=11	n=12
0	E	E	E	E	E	E	E	E	E	E	E
1	S	S	S	S	E	E	E	E	E	E	E
2	U	D	S	S	S	S	S	S	E	E	E
3		U	U	D	D	S	S	S	S	S	S
4			U	U	U	U	D	D	D	S	S
5				U	U	U	U	D	D	D	D
6					U	U	U	U	U	U	U
7						U	U	U	U	U	U

D: De-escalate the dose; E: Escalate the dose; S: Stay at the dose; U: Unacceptable toxicity

Note: If one patient has a DLT event observed in a dose cohort with 1 patient enrolled, additional patients (eg, 1 or 2) may be enrolled for dose escalation assessment.

Dose escalation will stop under any of the following conditions:

- The maximum sample size has been achieved;
- 6-12 patients have been enrolled at a dose that is predicted to be the MTD;
- All doses explored appear to be overly toxic and the MTD cannot be determined.

Intrapatient dose escalation, other than the potential inclusion of priming doses, will not be permitted in this study.

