3.4. MTD Definition

The estimated MTD is the dose level associated with approximately 27.5% of DLT-evaluable patients experiencing a DLT. The target interval for the DLT rate is (22.5%-32.5%). Due to the discreteness of the dose levels and in the interest of the safety of patients, the estimated MTD is the highest tested dose level with DLT rate ≤ 0.325 in at least 6-12 evaluable patients for DLT. The study aims to determine a MTD for a dose regimen that does not include a priming dose administered IV, and an independent MTD for an IV dose regimen that includes a priming dose. In addition, the study aims to determine a MTD for PF-06671008 administered SC and may also determine an independent MTD for a SC dose regimen that includes a priming dose.

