9.2. Statistical Methods and Properties

This study has been designed to establish the Maximum Tolerated Dose (MTD) defined as the dose that yields approximately 27.5% probability of DLT and considers equivalent doses that yield probability of DLT in the interval (Equivalence Interval) 22.5% to 32.5%. The 27.5% target was chosen based on safety considerations and is considered appropriate based on simulations and expert input. The prior distribution of DLT is set as a beta (0.5,0.5) and the threshold probability for early termination and dose exclusion is set to 0.95 as suggested

in the original mTPI method.¹¹ Similarly, doses with an incidence of DLT>32.5% (eg, 4 out of 10) cannot be selected as MTD although is allowed by the mTPI method.

The modified toxicity probability interval (mTPI) design uses a Bayesian statistics framework and a beta/binomial hierarchical model to compute the posterior probability of three dosing intervals that reflect the relative difference between the toxicity rate of each dose level to the target rate ($pT = 0.275$) (See [Appendix 7](#)). If the toxicity rate of the currently used dose level is far smaller than pT , the mTPI will recommend escalating the dose level; if it is close to pT , the mTPI will recommend continuing at the current dose; if it is far greater than pT , the mTPI will recommend de-escalating the dose level. These rules are conceptually similar to those used by the 3+3 design, except the decisions of an mTPI design are based on posterior probabilities calculated under a coherent probability model. Being a model-based design, mTPI automatically and appropriately tailors dose-escalation and de-escalation decisions for different trials with different toxicity parameters. More importantly, all the dose-escalation decisions for a given trial can be pre-calculated under the mTPI design and presented in a two-way table. The decision rules to “dose escalate” (E), “no change in dose” (S), “dose de-escalate” (D) or “dose de-escalate, unacceptable toxicity” (U) are described in [Table 2](#).

Table 6. Dose Escalation Levels for IV Administration

Dose Level	Dose (ng/kg)
1 (Starting Dose)	1.5
2	7.5
3	20
4	50
5	100
6	200
7	300
8	400

* Intermediate doses may be evaluated based on clinical findings (eg, a dose between 20 and 50 ng/kg).

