Cohorts of patients could receive doses already tested but a dose that is associated with decision “Dose de-escalate, unacceptable toxicity” cannot be revisited and no more patients should be treated at this dose or higher doses for the remainder of the trial.

The maximum sample size for Part 1 would be N=92 but actual sample size will depend on the underlying dose toxicity profile and variability in actual data realization.

The study will continue accruing until one of the three stopping conditions below is triggered.

The algorithm will stop if any of the following criteria is met:

1. The maximum sample size has been achieved.

2. MTD has been identified with sufficient accuracy: 6 to 12 patients have been accumulated on a dose that is currently estimated to be the MTD; or
3. All doses explored appear to be overly toxic and the MTD cannot be determined.

Due to binomial data variability in small samples, DLTs may be observed in a first cohort(s) by chance even when the true Probability (DLT) is fairly low. This could result in the estimated posterior DLT rate to exceed the targeted 27.5% very early in the trial, triggering an early stop when very few patients (2-4) have been treated. To prevent stopping the trial prematurely in such cases, a step-down option with a lower dose of 1.0 ng/kg is added to the dose grid. This dose will be explored only if a high DLT rate occurs in the first cohort assigned to 1.5 ng/kg, ie, it will not be used as a starting dose and the algorithm will always assign the first cohort of patients to 1.5 ng/kg.

The following table shows the probability of escalating to the next dose level for a range of underlying true DLT rates. For example, for a cohort size of n=3 and for a DLT that occurs in 10% of patients, there is a greater than 90% probability of escalating. Conversely, for a DLT that occurs with a rate of 70%, the probability of escalating is 3%. It is assumed that dose escalation occurs with either 0/3 or 1/6 patients with DLTs.

Probability of Escalating Dose

True underlying DLT rate	10%	20%	30%	40%	50%	60%	70%	80%	90%
Probability of escalating dose	0.91	0.71	0.49	0.31	0.17	0.08	0.03	0.009	0.001

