9.3. Sample Size Determination

This first in patient study is divided in to two parts. Up to approximately 152 patients are expected to be enrolled in the study overall.

In Part 1, patients will participate in a dose escalation phase aimed at estimating the MTD. The sample size for this component of the study will vary depending on the number of DLTs observed. It is anticipated that the maximum sample size of approximately 92 patients are expected to be enrolled in Part 1 of the study at approximately 6 sites. The actual number of patients enrolled will depend upon tolerability and the number of dose levels required to identify the MTD.

The minimum and maximum sample sizes after which Part 1 can be stopped and MTD declared are approximately 6-12 and approximately 92 patients, respectively. As for the number of patients treated at each dose, it is expected that the typical number will be 1 to 4 patients for the doses actually studied. However, since variable cohort size is allowed, the actual number of patients treated at each dose will vary from 1 to 12.

In Part 2 the maximum sample sizes for each tumor indication (ie, TNBC, CRC and NSCLC) will be in the range n=10 to n=20. Enrollment of patients in one indication may be discontinued if minimal or no anti-tumor activity (eg 0 or 1 response) is observed in the first 10 evaluable patients for that indication. Assuming a non-informative prior (ie, Jeffrey's prior) if 1 out of 10 patients have tumor response, this would predict a posterior probability

(Beta-Binomial) equal to 0.93 that the true response is inferior to 30%. On the other hand, if 7 out of 20 patients have tumor response, this would predict a posterior probability equal to 0.70 that the true response is not inferior to 30% and a posterior probability equal to 0.05 (5%) that the true response is inferior to 20%. In addition, posterior probabilities may be calculated by using informative priors based on the antitumor activity that may be observed during Part 1 (eg 2 out of 3 TNBC patients experience tumor response in Part 1). These posterior probabilities will be assessed for each indication during Part 2 when at least the first 10 Pts are enrolled in that indication. Posterior Probabilities >0.75 of an ORR<20% (eg, 0,1 out of 10; 0,1,2 out of 16) may provide evidence of no substantial anti-tumor activity for that indication.

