Appendix 7. Detailed Dose Escalation/De-Escalation Scheme for mTPI Design

Escalation/De-escalation algorithms for total number of patients treated at the current dose level (current and previous cohorts)

- With 1 patient treated at current dose level
 - 0 DLT -> escalate
 - 1 DLT or other toxicities occur (ie, those that have the potential to be DLTs if more severe) -> may add additional patients to asses safety on a cohort size of n=2-4
- With 2 patients treated at current dose level
 - 0 DLT -> escalate
 - 1 DLT -> remain at the same dose
 - 2 DLTs -> de-escalate and consider current dose as intolerable
- With 3 patients treated at current dose level
 - 0 DLT -> escalate
 - 1 DLT -> remain at the same dose
 - 2 DLTs -> de-escalate
 - 3 DLTs -> de-escalate and consider current dose as intolerable
- With 4 patients treated at current dose level
 - 0 DLT -> escalate
 - 1-2 DLTs -> remain at the same dose
 - 3-4 DLTs -> de-escalate and consider current dose as intolerable
- With 5 patients treated at current dose level
 - 0 DLT -> escalate
 - 1 DLT -> remain at the same dose
 - 2 DLTs -> remain at the same dose (mTPI suggests “escalate”)
 - 3 DLTs -> de-escalate

- 4-5 DLTs -> de-escalate and consider current dose as intolerable
- With 6 patients treated at current dose level
 - 0-1 DLT -> escalate
 - 2 DLTs -> remain at the same dose
 - 3 DLTs -> de-escalate
 - 4-6 DLTs -> de-escalate and consider current dose as intolerable
- With 7 patients treated at current dose level
 - 0-1 DLT -> escalate
 - 2-3 DLTs -> remain at the same dose
 - 4-7 DLTs -> de-escalate and consider current dose as intolerable
- With 8 patients treated at current dose level
 - 0-1 DLT -> escalate
 - 2-3 DLTs -> remain at the same dose
 - 4 DLTs -> de-escalate
 - 5-8 DLTs -> de-escalate and consider current dose as intolerable
- With 9 patients treated at current dose level
 - 0-1 DLT -> escalate
 - 2-3 DLTs -> remain at the same dose
 - 4 DLTs -> de-escalate (mTPI suggests “remain at the same dose”)
 - 5-9 DLTs -> de-escalate and consider current dose as intolerable

- With 10 patients treated at current dose level
 - 0-1 DLT -> escalate
 - 2-3 DLTs -> remain at the same dose
 - 4 DLTs -> de-escalate (mTPI suggests “remain at the same dose”)
 - 5 DLTs -> de-escalate
 - 6-10 DLTs -> de-escalate and consider current dose as intolerable
- With 11 patients treated at current dose level
 - 0-2 DLT -> escalate
 - 3-4 DLTs -> remain at the same dose

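### The dose-decision rules conflict in four of 73 cells: protocol Table 2 disagrees with Appendix 7 at 5/9 and 2/10, and SAP Table 2 repeats both and also departs from the protocol at 4/7 and 4/10

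*Protocol*

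**What the plan says.** Protocol section 9.2 sets the mTPI model: target DLT rate 0.275, equivalence interval 0.225-0.325 and a Beta(0.5, 0.5) prior. It adds that "the threshold probability for early termination and dose exclusion is set to 0.95 as suggested" in the original method. It also says that all decisions can be calculated in advance, and it points to Table 2 for them.

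Table 2 in section 3.2.2 is coded "D: De-escalate the dose; E: Escalate the dose; S: Stay at the dose; U: Unacceptable toxicity". Appendix 7 gives the same rules line by line for 1 to 12 patients. For nine patients it reads "5-9 DLTs -> de-escalate and consider current dose as intolerable". It marks some lines where the protocol departs from the model, for example "4 DLTs -> de-escalate (mTPI suggests" staying at the dose.

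U has a stronger consequence than D. Under section 9.2 a U dose "cannot be revisited and no more patients should be treated at this dose or higher doses for the remainder of the trial".

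SAP section 2.2.3 reprints Table 2. SAP section 1 says the SAP is based on the protocol dated 12 January 2018. SAP section 2 allows the SAP to modify the protocol's plans, but says that major changes to the primary endpoint or its analysis will also go into a protocol amendment.

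**The concern.** First-cycle DLT is the Part 1 primary endpoint, and these cells turn DLT counts into dosing decisions. Where two passages of one protocol give different actions for the same count, the team must choose after seeing the data, and nothing in the protocol says which passage governs.

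What is at stake is mainly exposure and dose closure:

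- **5/9 (protocol Table 2 and SAP) and 4/7 (SAP):** a dose that meets the plan's own exclusion rule stays available for a return.
- **2/10 (protocol Table 2 and SAP):** the next cohort is escalated where Appendix 7 holds the dose.
- **4/10 (SAP):** treatment continues at an observed 40% DLT rate where the protocol steps down.

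Naming a wrong MTD is not the main risk. By section 3.4, "the estimated MTD is the highest tested dose level with DLT rate" of at most 0.325, and section 9.3 says "the actual number of patients treated at each dose will vary from 1 to 12". The best results still possible within 12 patients are 4/12 = 0.333 from 4/7, 5/12 = 0.417 from 5/9 and 4/12 = 0.333 from 4/10. All exceed 0.325.

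**Working it through.** **Inputs** (protocol section 9.2 and Appendix 7, Table 10): prior Beta(0.5, 0.5); target 0.275; interval 0.225-0.325; exclusion threshold 0.95.

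**Rule.** With x DLTs in n patients the posterior is Beta(0.5+x, 0.5+n-x). The unit mass of an interval is its posterior probability divided by its length. The lengths are 0.225 (E), 0.100 (S) and 0.675 (D), and the largest unit mass gives the decision. If Pr(p>0.275) exceeds 0.95, the decision is U.

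**Cells compared.** For n = 2 to 12 and 0 to 7 DLTs there are 3+4+5+6+7 for n = 2 to 6, plus 6×8 for n = 7 to 12, so 25+48 = 73.

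**Reproducing the plan's grids.** Unmodified mTPI matches Appendix 7 in 68 cells. The other five (1/5, 4/9, 4/10, 5/11, 5/12) are all more conservative than the model. It matches protocol Table 2 in 66 cells: the same five differ, plus 5/9 and 2/10, which are less conservative than the model and carry no explanation. All three sources agree with one another in 69 cells. The four conflicts are:

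| DLTs/n | Protocol Table 2 | Appendix 7 | SAP Table 2 | mTPI |
|---|---|---|---|---|
| 4/7 | U | U | D | U |
| 5/9 | D | U | D | U |
| 2/10 | E | S | E | S |
| 4/10 | D | D | S | S |

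**Each cell.**

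- 4/7: Beta(4.5, 3.5), Pr(p>0.275) = 0.954, so U.
- 5/9: Beta(5.5, 4.5), Pr(p>0.275) = 0.964, so U.
- 2/10: Beta(2.5, 8.5). E = 0.5458/0.225 = 2.43; S = 0.2503/0.100 = 2.50; D = 0.2039/0.675 = 0.30. The answer is S, narrowly.
- 4/10: Beta(4.5, 6.5). E = 0.0978/0.225 = 0.43; S = 0.1991/0.100 = 1.99; D = 0.7031/0.675 = 1.04; Pr(p>0.275) = 0.815. The model says S. The protocol overrides it to D, and section 9.2 names 4 out of 10 as a rate that cannot be the MTD.

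A Beta(1, 1) prior gives the same four decisions. Each table row has its full number of entries, so a broken extraction is an unlikely cause.

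**Misplaced note.** For five patients Appendix 7 prints "2 DLTs -> remain at the same dose (mTPI suggests" escalation. At 2/5 the model gives S (S 1.74, E 0.75). It gives E at 1/5 (E 2.26, S 1.98), so the note appears to sit one line too low.

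**How often the cells are reached.** This is an exact recursion over (DLTs, n) for one uninterrupted stay at a dose, continuing only on S, up to 12 patients. As a hand check, take constant cohorts of 3. The only path to 5/9 is 1/3, then 2/6, then three DLTs in three, with probability (3p(1-p)²)²·p³. At p = 0.40 this is 0.432² × 0.064 = 0.012.

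With cohort sizes 2, 3 and 4 equally likely:

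| True DLT rate | 4/7 | 5/9 | 2/10 | 4/10 | 5/9 or 2/10 | Any of four |
|---|---|---|---|---|---|---|
| 0.20 | 0.004 | 0.001 | 0.030 | 0.012 | 0.031 | 0.046 |
| 0.275 | 0.010 | 0.002 | 0.026 | 0.023 | 0.028 | 0.062 |
| 0.40 | 0.026 | 0.007 | 0.012 | 0.033 | 0.019 | 0.079 |
| 0.50 | 0.037 | 0.011 | 0.004 | 0.027 | 0.015 | 0.080 |

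With constant cohorts of 2, only 2/10 and 4/10 can occur (together 0.047-0.080). With 3, only 5/9 can (0.001-0.018). With 4, none can. If a stay ends once six or more patients show a rate of at most 0.325, the in-protocol figure falls to 0.009-0.012. Ending at nine leaves it unchanged.

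**The case against.** The case for a lighter view accepts every cell and every figure. Its points are these:

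- **The documents largely settle the SAP-only cells.** Major changes to the primary endpoint or its analysis need a protocol amendment, and the SAP cites the current protocol as its basis. So 4/7 and 4/10 read as copying errors, and the protocol should prevail. This stands. Sites dose by the protocol, and the SAP's own DLT analysis only summarises and lists events, so these two cells matter little in conduct.
- **2/10 is nearly a tie.** The observed 20% lies below the interval, and after a first DLT the escalation steps are capped. This stands as to harm, but escalate and stay remain different instructions for one count.
- **At 5/9 both versions step down at once.** Extra exposure needs a later re-escalation and a decision to return, despite continuing safety review. This is fair: the figures measure reaching a cell, not being harmed.
- **The reach figures ignore the stop at 6-12 patients.** Applying it at six lowers them as shown. Section 9.3 also expects typically 1 to 4 patients per dose, and the opening cohorts of 1-2 were not modelled.
- **Calling 1/5 deliberate is inference.** Appendix 7 does not annotate that line, and a Beta(1, 1) prior also gives stay there. The sponsor should confirm it.

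None of this removes the 5/9 and 2/10 conflicts, which lie within the protocol itself and have no precedence rule.

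**Conclusion.** The concern holds. Two cells conflict inside the protocol, and SAP Table 2 is wrong against Appendix 7 in four. At 5/9, 4/7 and 2/10 the plan's own parameters support Appendix 7. At 4/10 the SAP matches the unmodified model but drops an override that the protocol declares.

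The most serious cell is 5/9. There the protocol's main table leaves open a dose that its own 0.95 rule would close, in a first-in-patient study of a T-cell-engaging agent with cytokine-release risk. The probability is small, about 1% to 3% per stay at a dose for an in-protocol conflict. That rests on mixed cohorts of 2-4, true DLT rates of 0.20-0.50 and no return visits, and the lower end applies if escalation stops at six patients. The figure is per stay, and the study plans eight IV dose levels and up to four regimens. A dose-closure rule with two printed answers should be corrected before it is applied, however rarely the cell is reached.

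**What to change.** Make all three passages match Appendix 7.

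- **Protocol Table 2:** 5/9 from D to U; 2/10 from E to S.
- **SAP Table 2:** 4/7 and 5/9 from D to U; 2/10 from E to S; 4/10 from S to D.
- **Appendix 7:** move the note about escalation from 2/5 to 1/5, once the sponsor confirms that staying at 1/5 is intended.
- **Footnote under the table:** list the departures from mTPI, namely 1/5 stay (model E), and 4/9, 4/10, 5/11 and 5/12 de-escalate (model S).

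The cost is six cell edits, one moved note and one footnote. It needs no extra patients and no change to the design.

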 - 5 DLTs -> de-escalate (mTPI suggests “remain at the same dose”)
 - 6-11 DLTs -> de-escalate and consider current dose as intolerable
- With 12 patients treated at current dose level
 - 0-2 DLTs -> escalate
 - 3-4 DLTs -> remain at the same dose
 - 5 DLTs -> de-escalate (mTPI suggest “remain at the same dose”)
 - 6-12 DLTs -> de-escalate and consider current dose as intolerable

mTPI Operating Characteristics

This is a dose-escalation study primarily driven by safety. While efficacy endpoints will also be assessed, they will play only a supportive role. The primary safety endpoint will be presence or absence of DLT. The simulation focuses on a follow-up period for DLT assessment and ignores non DLTs toxicities or DLTs occurring outside of this time frame. This simulation refer to the escalation phase after the selection of the priming dose as that will be based on non DLTs lower grade cytokine release (eg < Grade 2; see [Evaluation of a Priming Dose](#)).

This study has been designed to establish the Maximum Tolerated Dose (MTD) defined as the dose that yields approximately 27.5% probability of DLT and considers equivalent doses that yield probability of DLTs in the interval (Equivalence Interval) 22.5% to 32.5%. The 27.5% target was chosen based on safety considerations and is considered appropriate based on simulations and expert input. Since mTPI algorithms are known to assign more patients

above the target dose compared to 3+3 designs, the target was chosen slightly below the maximum acceptable DLT rate of 33.3% (in order to protect study patients from exposure to doses with DLT rate higher than 33%). Doses with an incidence of DLT>33% cannot be selected as MTD in the current protocol therefore the decision rules implemented in the actual study are more conservative of the ones used in this simulation, therefore results of these simulations represent more aggressive scenario. In addition, in the study patients will be enrolled in cohorts of size 2-4 but constant size of 3 was assumed for all simulations.

Table 10. Simulation Parameters Selected for the Final Design

	Final Design Value
Control Parameters	
Cohort size	3 patients
Max doses levels	5 levels
Minimum number of patients on MTD to stop for success	6,9,12 patients
Other parameters	
Max sample size for one regimen of part 1	50 patients
DLT target rate at MTD	pT= 0.275
Equivalence Interval for DLT target rate at MTD	EI: 0.225-0.325
Prior distribution of DLT	Beta(0.5,0.5)

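### The decision grids say Stay at 4 DLTs in 11 or 12 patients, a rate above the 0.325 MTD cap that cannot come down within the stated 1 to 12 patients per dose, and at 4/12 they give no next step

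*Protocol*

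**What the plan says.** **Decision cells.** The decision for 4 DLTs, by number of patients treated at the dose:

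| Source | n=9 | n=10 | n=11 | n=12 |
|---|---|---|---|---|
| Protocol 3.2.2, Table 2 | D | D | S | S |
| Protocol Appendix 7 | D (overrides mTPI) | D (overrides mTPI) | S | S |
| SAP 2.2.3, Table 2 | D | S | S | S |

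The Appendix 7 entry for both 11 and 12 patients reads "3-4 DLTs -> remain at the same dose".

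**MTD cap.** Protocol 3.4, repeated almost word for word in SAP 2.2.4: "the estimated MTD is the highest tested dose level with DLT rate ≤ 0.325 in at least 6-12 evaluable patients for DLT". Protocol 9.2: "doses with an incidence of DLT>32.5% (eg, 4 out of 10) cannot be selected as MTD although is allowed by the mTPI method". Appendix 7 uses a different figure. It excludes doses above 33% and describes 33.3% as the maximum acceptable DLT rate.

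**Patients per dose.** Protocol 9.3 and SAP 5.2.1: "the actual number of patients treated at each dose will vary from 1 to 12". No scheme has a rule beyond n=12.

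**Stopping.** Part 1 stops at the maximum sample size, when all explored doses appear too toxic, or when "6 to 12 patients have been accumulated on a dose that is currently estimated to be the MTD" (protocol 9.2).

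**The concern.** The three schemes agree at 4/11 and 4/12, so these two cells are not a transcription slip between documents. The conflict is between the decision rule and the MTD definition. At 4/11 the rule sends further patients to a dose that cannot meet the 0.325 cap by n=12. At 4/12 it says Stay when the stated range is used up, and none of the stopping conditions need apply.

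Appendix 7 replaces the mTPI's own Stay with de-escalation at 4/9, 4/10, 5/11 and 5/12. It leaves Stay at 4/11 and 4/12 without comment, so a reader cannot tell whether this was intended.

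At stake are the Part 1 primary objective, which is estimation of the MTD, and the exposure of patients at a dose that may not be selectable. The protocol's Tables 12 and 13 do not show the problem, because Appendix 7 says the simulated rules are less conservative than those implemented with the cap.

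**Working it through.** **1. Reproduce the plan's decision.** Inputs from protocol 9.2: prior Beta(0.5, 0.5), equivalence interval 0.225-0.325, target 0.275, exclusion threshold 0.95. The posterior is Beta(0.5+x, 0.5+n-x). Each interval's unit probability mass is its posterior probability divided by its width (0.225, 0.100, 0.675), and the largest decides.

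| x/n | Escalate | Stay | De-escalate | P(p>0.275) | Result |
|---|---|---|---|---|---|
| 4/10 | 0.43 | 1.99 | 1.04 | 0.815 | Stay |
| 4/11 | 0.61 | 2.43 | 0.92 | 0.754 | Stay |
| 4/12 | 0.80 | 2.80 | 0.80 | 0.688 | Stay |

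All three Stay entries are therefore correct as plain mTPI output. They simply do not carry the cap.

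**2. Apply the cap.** 4/10 = 0.400, 4/11 = 0.364 and 4/12 = 0.333 all exceed 0.325. The most DLTs allowed are 0.325 × 11 = 3.58, so 3, and 0.325 × 12 = 3.90, so 3. Since 4/0.325 = 12.3, four DLTs first comply at n=13 (4/13 = 0.308).

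**3. Look for other stuck cells.** DLT counts cannot fall, so the best rate a cell can reach by n=12 is x/12. The other above-cap Stay cells (1/2, 1/3, 2/4, 2/5, 2/6, 3/7, 3/8, 3/9) can reach 1/12, 2/12 or 3/12 = 0.250 and so can recover. In the protocol only 4/11 and 4/12 cannot. SAP Table 2 adds 4/10.

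**4. Check the stopping conditions at 4/12.** The dose is not MTD-eligible under 0.325. The Part 1 maximum (about 92) need not have been reached. Lower doses need not be too toxic.

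**5. Reach the cells at one dose, true DLT rate 0.275.** This follows one uninterrupted run of Stay decisions under the Appendix 7 rules. A dose is declared the MTD once it has the stopping number of patients and a rate of 0.325 or less.

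- *Cohorts of 3, 6- or 9-patient stop.* The only path is 1/3, 2/6, 3/9, 4/12, with one DLT per cohort: P(1 of 3) = 3 × 0.275 × 0.725² = 0.4336, and 0.4336⁴ = 0.035. With the 12-patient stop, a path through 2/9 adds 0.4336² × 0.3811 × 0.1645 = 0.012, giving 0.047.
- *True rates 0.225 to 0.325, all three stops.* P(4/12) is 2.7-5.2% with cohorts of 3 and 6.4-15.6% with cohorts of 4. With cohorts of 2 it is 0 when stopping at 6 or 9, and 2.4-3.5% when stopping at 12.
- *4/11* cannot occur with cohorts of 3 alone. With cohorts of 3, 4, 4 as an illustration, the path through 3/7 has probability 0.4336 × 0.2385 × 0.4192 = 0.043. With a 9- or 12-patient stop the path through 2/7 adds the same again, giving 0.087.

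**6. Whole trials.** One simulation used the Appendix 7 rules, cohorts of 3, five levels, at most 50 patients, the 0.325 cap, 12 patients per dose, the 9-patient stop and 20,000 trials per scenario:

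| Scenario | Reaches 4/12 | of which a lower dose has ≥6 patients at ≤0.325 | Share with no such dose |
|---|---|---|---|
| 1 | 0.024 | 0.017 | 32% |
| 2 | 0.134 | 0.099 | 26% |
| 3 | 0.161 | 0.114 | 29% |
| 4 | 0.168 | 0.089 | 47% |
| 5 | 0.199 | 0.023 | 88% |

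The protocol does not fix every assumption such a simulation needs, notably re-escalation. Varying them, still with cohorts of 3 and the 9-patient stop, gives about 1-3% in Scenario 1 and 7-20% in Scenarios 2-5. Barring re-escalation to a dose already graded D or U left no qualifying lower dose in 51-90% of the trials that ended at 4/12. Over cohort sizes 2-4, stopping numbers 6-12 and the re-escalation assumptions, the share reaching 4/12 runs from 0 to about 28%.

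**The case against.** A reader might infer that any trial reaching 4/12 ends without an MTD, or that such a dose can never become the MTD. The documents do not support either statement in that form, for three reasons, each of which stands in part.

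- **Fallback.** Section 3.4 names the highest tested dose that meets the cap. Protocol 9.2 lets cohorts return to doses already tested, and 3.2.2 assigns patients to the dose closest to the current MTD prediction. If a lower dose has at least 6 evaluable patients at 0.325 or less, it can be named. But the grid says Stay and does not direct this, and such a dose is often absent.
- **Twelve patients.** The figure stands in sample-size text and is not a stopping rule. Section 3.4 sets a minimum, not a ceiling. Section 3.2 allows additional patients at or below the MTD and uses their safety profile in establishing it. But it also says their DLTs may be left out of the algorithm, and no table column covers n=13.
- **Cap wording.** If the operative limit is the 33.3% in Appendix 7, 4/12 sits exactly on it and Stay may be deliberate. Taken literally, though, that appendix's exclusion above 33% still catches 4/12. At 36.4%, 4/11 is over on any reading, as is 4/10 in the SAP.

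It is also fair to say that 4/12 exceeds 0.325 by only 0.008, and that protocol 9.7 has the sponsor and investigators review each dose level. That review could resolve a case, but by judgement and not by the stated rule.

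**Conclusion.** The inconsistency is real and follows from division alone. Read with the 0.325 cap and the 1 to 12 patients per dose, the schemes say Stay at counts that cannot qualify: 4/11 and 4/12 in both documents, and 4/10 in the SAP as well. At 4/12 no next step is given. It is a gap in the decision grid at that dose, and does not mean that Part 1 necessarily fails to find an MTD.

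The conclusion for 4/12 rests on the 0.325 cap, since the Appendix 7 wording would make that cell borderline. The conclusion for 4/11 holds under either cap. Both rest on taking 12 as the upper end of the per-dose range. The frequency depends on cohort size, stopping number and re-escalation assumptions, so it should be quoted only as the ranges in the working: small in Scenario 1, and large enough to plan for in Scenarios 2-5.

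**What to change.** Reconcile the following so that they agree:

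- the 4/11 and 4/12 cells in protocol 3.2.2 Table 2, Appendix 7 and SAP 2.2.3 Table 2, and the 4/10 cell in SAP Table 2, which differs from the protocol;
- the MTD cap: 0.325 in protocol 3.4 and 9.2 and SAP 2.2.4, against 33% and 33.3% in Appendix 7;
- the per-dose range in protocol 9.3 and SAP 5.2.1, saying whether 12 is a limit or an expectation.

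The scheme should then state what follows each of these counts, including how the section 3.4 fallback to a lower dose is to operate. Which rule prevails is for the sponsor to decide.

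The cost is a few table cells and a sentence or two in the next protocol amendment, with a matching SAP update. The clarification itself does not require a larger planned sample size.
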